#### 10.1.1 Definitions

Evaluable for toxicity. All patients will be evaluable for toxicity from the time of their first treatment with regorafenib.

Evaluable for objective response. Only those patients who have measurable disease present at baseline, have received at least one cycle of therapy, and have had their disease re-evaluated will be considered evaluable for response. These patients will have their response classified according to the definitions stated below. (Note: Patients who exhibit objective disease progression prior to the end of cycle 1 will also be considered evaluable.)

Evaluable Non-Target Disease Response. Patients who have lesions present at baseline that are evaluable but do not meet the definitions of measurable disease, have received at least one cycle of therapy, and have had their disease re-evaluated will be considered evaluable for non-target disease. The response assessment is based on the presence, absence, or unequivocal progression of the lesions.

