Study design	Patients with advanced and metastatic biliary tract adenocarcinoma (cholangiocarcinoma) who had been treated with and failed first-line chemotherapy will be treated with regorafenib (120 mg) orally once daily 21 days (3 weeks) on and 7 days (1 week) off in the 28-day (4-week) cycle.
Type of control	Single arm uncontrolled

Number of subjects	Maximum of 37 patients.
Plan for statistical analysis	
There will be no stratification. OR will be estimated at end of trial with 95% exact binomial confidence intervals. PFS and OS will be estimated by the Kaplan-Meier method, with appropriate 90% confidence intervals. Toxicity events will be tabulated. Change in CA19-9 and CEA will be characterized by their mean changes, with a nonparametric CDF-based 90% confidence interval. The study will have 83% power (using a one-sided test at <math>\alpha=0.10</math>) to reject the null hypothesis (PFS<2.0 months) if the true median PFS is at least 3.5 months.

Schema:

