#### 10.1.4.3 Evaluation of Best Overall Response

The best overall response is the best response recorded from the start of the treatment until disease progression/recurrence (taking as reference for progressive disease the smallest measurements recorded since the treatment started). The patient's best response assignment will depend on the achievement of both measurement and confirmation criteria.

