#### **12.1.2 Secondary objectives**

- Overall response rate (ORR), including complete and partial response. The ORR at four months will be estimated with an exact 90% binomial confidence interval.
- Overall survival (OS). The overall survival function will be estimated by the Kaplan-Meier method, with a 90% confidence interval.
- DCR (disease control rate) as ORR plus stable disease (SD)
- Measurable changes in biomarkers (CA19-9 and CEA), in patients that were elevated at the time of registration. The means and standard deviation of both markers will be estimated at before and after treatment. The null hypothesis of no treatment effect will be tested using a paired-comparison t-test ( $\alpha=0.10$ ), or a rank sum test if there is evidence of significant non-normality in the differences.
- Evaluation of safety and associated toxicities. Toxicities will be tabulated by grade and type.

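### The objective response rate (ORR) has conflicting interval levels and an unclear time frame, and neither ORR nor the disease control rate (DCR) has a stated denominator

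*Combined protocol and SAP*

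**What the plan says.** On the estimate, the synopsis states: "OR will be estimated at end of trial with 95% exact binomial confidence intervals". Section 12.1.2 states: "The ORR at four months will be estimated with an exact 90% binomial confidence interval". Section 12.1.2 forms DCR by adding stable disease to the responders and gives it no interval and no time point. Section 10.1.4.3 defines the patient-level outcome over the whole treatment course: "The best overall response is the best response recorded from the start of the treatment until disease progression/recurrence".

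On who is counted, neither the synopsis nor section 12.1.2 names an analysis set for ORR or DCR. Section 6, in contrast, does name the safety set (at least one dose). Section 10.1.1 limits the patients whose response can be assessed, as follows: "Only those patients who have measurable disease present at baseline, have received at least one cycle of therapy, and have had their disease re-evaluated". Its note adds one exception: "Patients who exhibit objective disease progression prior to the end of cycle 1 will also be considered evaluable". The parallel set for non-target disease has the same two filters: "have received at least one cycle of therapy, and have had their disease re-evaluated will be considered evaluable for non-target disease". No text ties either set to section 12.1.2.

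On timing, sections 9 and 10.1 place scans every two cycles, up to 3 days before day 1 of each odd cycle. An End of Treatment scan follows 28 days (±5) after the last dose. Section 9 also allows a ±1 week scheduling window and lets each later cycle start up to a week late. Under section 10.1.6 death is a PFS event. Section 3.5 lets dropouts be replaced. Measurable disease is not an entry criterion in section 3.1.

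**The concern.** Two analysts following the current text could report different ORR intervals, count different responses, and divide by different numbers of patients. In a single-arm trial where section 10.1.7 gives the response review to the principal investigator, a denominator left open can be settled after the data are seen.

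The set that section 10.1.1 offers is selected on outcome. A patient with measurable disease who dies before any repeat scan, without objective progression, is a failure for PFS but would not appear in ORR or DCR. A patient who stops during cycle 1 without objective progression in that cycle would also disappear, whatever a later scan shows. Removing mostly unfavourable outcomes from the denominator raises both rates.

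**Working it through.** **The plan's own figure.** The documents give no expected rate or precision for ORR or DCR. Their one design figure is 83% power for PFS (37 patients, medians 2.0 and 3.5 months, one-sided alpha 0.10). One approximation reproduces it: with exponential PFS, S(2.0) under the alternative is 0.5^(2/3.5) = 0.673, and Φ[(0.673 − 0.5)/√(0.673 × 0.327/37) − 1.282] = 0.832. No response rate enters it, so nothing below changes it.

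**1. Interval level.** Exact (Clopper-Pearson) limits are the α/2 quantile of Beta(x, n−x+1) and the 1−α/2 quantile of Beta(x+1, n−x). The counts are assumed.
- 4/37 = 10.8%: 90% limits 3.8-23.1%, 95% limits 3.0-25.4%.
- 18/37 = 48.6% (for DCR): 90% limits 34.3-63.2%, 95% limits 31.9-65.6%.

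**2. Time frame.** Four months is 4 × 30.4375 = 121.75 days. With no delays the scheduled scans fall on elapsed days 53-56, 109-112 and 165-168. A response first seen at the third scan (about 5.5 months) counts towards best overall response but not towards a rate at four months.

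**3. Can the End of Treatment scan bring cycle-1 stoppers back under the exception?** The exception needs objective progression by day 28. With last dose on day d, the earliest scan is:
- d + 28 − 5 = d + 23 under the ±5-day allowance: by day 28 only if d ≤ 5.
- d + 28 − 7 = d + 21 under the ±1 week window: only if d ≤ 7.
- d + 28 − 12 = d + 16 if the two allowances stack: only if d ≤ 12.

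No routine scan is scheduled in cycle 1, so the exception will seldom apply to these patients. For patients who completed cycle 1, a later scan, including the End of Treatment scan, can still make them evaluable.

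**4. Deaths before the first scan.** The probability of death by day t is 1 − 2^(−(t/m)^k), where m is median survival in days. Section 2.1 gives a second-line median of 4-6 months (121.75 to 182.6 days). The shape k is assumed: 1 is exponential, and 2 gives fewer early deaths.

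| First scan | k = 1 | k = 2 |
|---|---|---|
| Days 46-49 (one week early) | 16.0-24.3% | 4.3-10.6% (1.6-3.9 of 37) |
| Days 53-56 (on schedule) | 18.2-27.3% (6.7-10.1 of 37) | 5.7-13.6% (2.1-5.0 of 37) |
| Days 67-70 (two one-week delays in every patient) | 22.5-32.9% (8.3-12.2 of 37) | 8.9-20.5% (3.3-7.6 of 37) |

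The exponential column is a high-end scenario, because entry requires ECOG 0-1 and a life expectancy of at least 12 weeks. These are deaths, not exclusions: some of these patients would progress objectively first and stay evaluable. Cycle-1 stoppers who do not die are not counted here.

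**5. Effect on the rates.** Illustration with all 37 measurable, 18 controlled, 4 responders, and an assumed 2 to 5 uncontrolled patients excluded:
- DCR: 18/37 = 48.6% becomes 18/35 = 51.4% to 18/32 = 56.3%.
- ORR: 4/37 = 10.8% becomes 4/35 = 11.4% to 4/32 = 12.5%.
- Opposite direction: excluding one cycle-1 stopper whose later scan shows stable disease gives DCR 17/36 = 47.2%. Excluding one with a partial response gives ORR 3/36 = 8.3%.

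**The case against.** The strongest reply is that the bias is conditional. If section 10.1.1 governs, the denominator is prespecified and the dispute is about convention. If it does not, the fault is a missing cross-reference and no bias has been shown. That stands in part. A reader might infer that the plan has adopted the evaluable-only denominator, because nothing else is on offer, but no text links it to section 12.1.2. What the documents support is the omission, and the likely direction of bias if that set is used.

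A reader might also infer an outright contradiction between a rate at the end of the trial and a rate at four months. The synopsis phrase may say only when the analysis is run, so that clash is not established. Nor is section 10.1.4.3 itself an ORR analysis rule: it defines a patient's best response and can coexist with a four-month rate. What remains is that the plan does not say which of the two ORR reports.

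A reader might take 2 to 5 patients as the expected number of exclusions. It is not. It matches a count of deaths under one assumed survival shape, and the response counts are invented for illustration. The illustrated shifts are also small against precision: 0.6-1.7 points of ORR against a 90% interval about 19 points wide.

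Finally, section 10.1.4.3 says that "best response assignment will depend on the achievement of both measurement and confirmation criteria", from which one might infer that only confirmed responses count. The footnote to its response table limits that requirement to trials with response as the primary endpoint, which this is not. I make nothing of this.

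**Conclusion.** The point holds as a minor correction. The two interval levels for ORR conflict in current text, and that finding needs no assumption. It is equally plain that DCR has no interval, that neither rate has a named denominator, and that a four-month rate can differ from best overall response.

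Upward bias is probable but conditional on the section 10.1.1 set being used, and its size cannot be fixed from the documents. Deaths by a first scan on days 46-56 range from about 4% to 27% across the assumed shapes and the quoted 4-6 month median, and this is not a bound on exclusions in either direction. A reader might infer that the trial's main conclusion is at risk. It is not: ORR and DCR are secondary and descriptive with no decision rule, early deaths already count in PFS, and the primary test and its stated power are unchanged.

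**What to change.** Amend section 12.1.2 and the synopsis together:
- Use one exact interval level for ORR in both places, and give DCR the same interval.
- State one time frame: best overall response as defined in section 10.1.4.3.
- Set the denominator for ORR and DCR as all dosed patients with measurable disease at baseline, including dropouts who were replaced under section 3.5.
- Count patients with no post-baseline assessment as non-responders and not controlled, labelled as a conservative convention. Classify cycle-1 stoppers who are scanned later by that scan.
- Report patients with only non-measurable disease separately, using the categories in the non-measurable table of section 10.1.4.3.
- Keep the section 10.1.1 evaluable-only rate as a labelled sensitivity analysis.

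The cost is wording only, with no added patients or procedures. The reported rates are likely to be slightly less favourable: about 3-8 points for DCR and 0.6-1.7 points for ORR in the illustration, or slightly more favourable if an early stopper later shows response or stable disease.

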#### 10.1.2 Disease Parameters

Measurable disease. Measurable lesions are defined as those that can be accurately measured in at least one dimension (longest diameter to be recorded) as  $\geq 20$  mm by chest x-ray or as  $\geq 10$  mm with CT scan, MRI, or calipers by clinical exam. All tumor measurements must be recorded in millimeters (or decimal fractions of centimeters).

Note: Tumor lesions that are situated in a previously irradiated area might or might not be considered measurable. *If the investigator thinks it appropriate to include them, the conditions under which such lesions should be considered must be defined in the protocol.*

Malignant lymph nodes. To be considered pathologically enlarged and measurable, a lymph node must be  $\geq 15$  mm in short axis when assessed by CT scan (CT scan slice

thickness recommended to be no greater than 5 mm). At baseline and in follow-up, only the short axis will be measured and followed.

**Non-measurable disease.** All other lesions (or sites of disease), including small lesions (longest diameter < 10 mm or pathological lymph nodes with  $\geq 10$  to < 15 mm short axis), are considered non-measurable disease. Bone lesions, leptomeningeal disease, ascites, pleural/pericardial effusions, lymphangitis cutis/pulmonitis, inflammatory breast disease, and abdominal masses (not followed by CT or MRI), are considered as non-measurable.

Note: Cystic lesions that meet the criteria for radiographically defined simple cysts should not be considered as malignant lesions (neither measurable nor non-measurable) since they are, by definition, simple cysts.

‘Cystic lesions’ thought to represent cystic metastases can be considered as measurable lesions, if they meet the definition of measurability described above. However, if non-cystic lesions are present in the same patient, these are preferred for selection as target lesions.

**Target lesions.** All measurable lesions up to a maximum of 2 lesions per organ and 5 lesions in total, representative of all involved organs, should be identified as **target lesions** and recorded and measured at baseline. Target lesions should be selected on the basis of their size (lesions with the longest diameter), be representative of all involved organs, but in addition should be those that lend themselves to reproducible repeated measurements. It may be the case that, on occasion, the largest lesion does not lend itself to reproducible measurement in which circumstance the next largest lesion which can be measured reproducibly should be selected. A sum of the diameters (longest for non-nodal lesions, short axis for nodal lesions) for all target lesions will be calculated and reported as the baseline sum diameters. If lymph nodes are to be included in the sum, then only the short axis is added into the sum. The baseline sum diameters will be used as reference to further characterize any objective tumor regression in the measurable dimension of the disease.

**Non-target lesions.** All other lesions (or sites of disease) including any measurable lesions over and above the 5 target lesions should be identified as **non-target lesions** and should also be recorded at baseline. Measurements of these lesions are not required, but the presence, absence, or in rare cases unequivocal progression of each should be noted throughout follow-up.

#### 10.1.3 Methods for Evaluation of Measurable Disease

All measurements should be taken and recorded in metric notation using a ruler or calipers. All baseline evaluations should be performed as closely as possible to the beginning of treatment and never more than 4 weeks before the beginning of the treatment.

The same method of assessment and the same technique should be used to characterize each identified and reported lesion at baseline and during follow-up. Imaging-based evaluation is preferred to evaluation by clinical examination unless the lesion(s) being followed cannot be imaged but are assessable by clinical exam.

Clinical lesions Clinical lesions will only be considered measurable when they are superficial (e.g., skin nodules and palpable lymph nodes) and  $\geq 10$  mm diameter as assessed using calipers (e.g., skin nodules). In the case of skin lesions, documentation by color photography, including a ruler to estimate the size of the lesion, is recommended.

Chest x-ray Lesions on chest x-ray are acceptable as measurable lesions when they are clearly defined and surrounded by aerated lung. However, CT is preferable.

Conventional CT and MRI This guideline has defined measurability of lesions on CT scan based on the assumption that CT slice thickness is 5 mm or less. If CT scans have slice thickness greater than 5 mm, the minimum size for a measurable lesion should be twice the slice thickness. MRI is also acceptable in certain situations (e.g. for body scans).

Use of MRI remains a complex issue. MRI has excellent contrast, spatial, and temporal resolution; however, there are many image acquisition variables involved in MRI, which greatly impact image quality, lesion conspicuity, and measurement. Furthermore, the availability of MRI is variable globally. As with CT, if an MRI is performed, the technical specifications of the scanning sequences used should be optimized for the evaluation of the type and site of disease. Furthermore, as with CT, the modality used at follow-up should be the same as was used at baseline and the lesions should be measured/assessed on the same pulse sequence. It is beyond the scope of the RECIST guidelines to prescribe specific MRI pulse sequence parameters for all scanners, body parts, and diseases. Ideally, the same type of scanner should be used and the image acquisition protocol should be followed as closely as possible to prior scans. Body scans should be performed with breath-hold scanning techniques, if possible.

PET-CT At present, the low dose or attenuation correction CT portion of a combined PET-CT is not always of optimal diagnostic CT quality for use with RECIST measurements. However, if the site can document that the CT performed as part of a PET-CT is of identical diagnostic quality to a diagnostic CT (with IV and oral contrast), then the CT portion of the PET-CT can be used for RECIST measurements and can be used interchangeably with conventional CT in accurately measuring cancer lesions over time. Note, however, that the PET portion of the CT introduces additional data which may bias an investigator if it is not routinely or serially performed.

Ultrasound Ultrasound is not useful in assessment of lesion size and should not be used as a method of measurement. Ultrasound examinations cannot be reproduced in their entirety for independent review at a later date and, because they are operator dependent, it cannot be guaranteed that the same technique and measurements will be taken from one assessment to the next. If new lesions are identified by ultrasound in the course of the

study, confirmation by CT or MRI is advised. If there is concern about radiation exposure at CT, MRI may be used instead of CT in selected instances.

Endoscopy, Laparoscopy The utilization of these techniques for objective tumor evaluation is not advised. However, such techniques may be useful to confirm complete pathological response when biopsies are obtained or to determine relapse in trials where recurrence following complete response (CR) or surgical resection is an endpoint.

Tumor markers Tumor markers alone cannot be used to assess response. If markers are initially above the upper normal limit, they must normalize for a patient to be considered in complete clinical response.

#### 10.1.4 Response Criteria

##### 10.1.4.1 Evaluation of Target Lesions

Complete Response (CR): Disappearance of all target lesions. Any pathological lymph nodes (whether target or non-target) must have reduction in short axis to <10 mm.

Partial Response (PR): At least a 30% decrease in the sum of the diameters of target lesions, taking as reference the baseline sum diameters.

Progressive Disease (PD): At least a 20% increase in the sum of the diameters of target lesions, taking as reference the smallest sum on study (this includes the baseline sum if that is the smallest on study). In addition to the relative increase of 20%, the sum must also demonstrate an absolute increase of at least 5 mm. (Note: the appearance of one or more new lesions is also considered progressions).

Stable Disease (SD): Neither sufficient shrinkage to qualify for PR nor sufficient increase to qualify for PD, taking as reference the smallest sum diameters while on study.

##### 10.1.4.2 Evaluation of Non-Target Lesions

Complete Response (CR): Disappearance of all non-target lesions and normalization of tumor marker level. All lymph nodes must be non-pathological in size (<10 mm short axis).

Note: If tumor markers are initially above the upper normal limit, they must normalize for a patient to be considered in complete clinical response.

Non-CR/Non-PD: Persistence of one or more non-target lesion(s) and/or maintenance of tumor marker level above the normal limits.

Progressive Disease (PD): Appearance of one or more new lesions and/or

*unequivocal progression* of existing non-target lesions. *Unequivocal progression* should not normally trump target lesion status. It must be representative of overall disease status change, not a single lesion increase.

Although a clear progression of “non-target” lesions only is exceptional, the opinion of the treating physician should prevail in such circumstances, and the progression status should be confirmed at a later time by the review panel (or Investigator).

#### 10.1.4.3 Evaluation of Best Overall Response

The best overall response is the best response recorded from the start of the treatment until disease progression/recurrence (taking as reference for progressive disease the smallest measurements recorded since the treatment started). The patient's best response assignment will depend on the achievement of both measurement and confirmation criteria.

#### For Patients with Measurable Disease (i.e., Target Disease)

Target Lesions	Non-Target Lesions	New Lesions	Overall Response	Best Overall Response when Confirmation is Required*
CR	CR	No	CR	≥4 wks. Confirmation**
CR	Non-CR/Non-PD	No	PR	≥4 wks. Confirmation**
CR	Not evaluated	No	PR	
PR	Non-CR/Non-PD/not evaluated	No	PR	Documented at least once ≥4 wks. from baseline**
SD	Non-CR/Non-PD/not evaluated	No	SD	
PD	Any	Yes or No	PD	no prior SD, PR or CR
Any	PD***	Yes or No	PD	
Any	Any	Yes	PD	

\* See RECIST 1.1 manuscript for further details on what is evidence of a new lesion.

\*\* Only for non-randomized trials with response as primary endpoint.

\*\*\* In exceptional circumstances, unequivocal progression in non-target lesions may be accepted as disease progression.

Note: Patients with a global deterioration of health status requiring discontinuation of treatment without objective evidence of disease progression at that time should be reported as “*symptomatic deterioration*.” Every effort should be made to document the objective progression even after discontinuation of treatment.

